Table 2: Cumulative incidence % by age (95% confidence interval)		
Age, y	Persistent TGA	Celiac disease#
5	2.4 (1.8-3.2)	1.7 (1.2-2.4)
10	4.3 (3.5-5.3)	3.1 (2.4-4.0)
15	5.1 (4.2-6.1)	3.3 (2.6-4.2)
#positive biopsy or high-titer TGA		

shows that, in the general population, the cumulative incidence of TGA and CD is approximately twice that of IA and T1D.

Multiple autoimmune phenotypes DAISY has previously reported that 23.8% (20.7-27.2%) of participants developed at least one autoimmune marker: IA, celiac, thyroid, adrenal, and rheumatoid autoimmunity by age 12 and hypothesized that at least 7% of Denver children express one or more of the autoimmune phenotypes by age 18 y. To balance administrative reduction of the budget, measurements of thyroid, adrenal, rheumatic and parietal autoantibodies on stored samples, was postponed until most of the cohort reaches the age of 20 y. T1D and CD are of particular interest as their detection at a pre-clinical stage meets the WHO criteria for large-scale screening. We have piloted a screening in general pediatric care clinics and have been invited by the JDRF and the Helmsley Charitable Trust to develop a demonstration project to screen 70,000 Denver children for IA and TGA. DAISY has shown that early detection of IA and education on diabetes symptoms can prevent diabetic ketoacidosis (DKA) and ~80% of hospitalizations at onset of T1D. This is important as the proportion of children presenting with DKA is on the rise.

Persistent IA developing after age 7 progresses more slowly to diabetes than early-onset IA and is associated with different dietary exposures. Early-onset IA developed in 143 subjects; late-onset IA developed in 65. Late-onset IA was less likely to initially present with multiple autoantibodies (15% vs. 32%,  $p=0.011$ ), spread to additional autoantibodies (**Figure 2**) or progress to T1D ( $p=0.01$ ) than early IA. Children with late-onset IA were less likely to have a sibling with T1D (12% vs. 27%,  $p=0.004$ ) or be non-Hispanic white (14% vs. 32% vs. 14%,  $p=0.002$ ). However, the frequencies of the HLA-DR3/4,DQB1\*03:02 genotype or T1D-associated SNPs in BACH2, CTLA4, ERBB3, GLIS3, GSDM/ORMDL3, IL27, IL2RA, INS, MICA, PTPN22, UBASH3A, IFIH1 and CLEC16A did not differ between early and late IA.

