## **Specific Aim 2. Validate candidate proteomic biomarkers of IA and T1D, in a nested-case study of 213 youth with persistent IA and 213 controls.**

**SIGNIFICANCE:** Progress in proteomic technology has made it applicable to epidemiologic studies. Prospective evaluation of the proteome contemporary with development of IA, or progression to T1D can help to discover underlying pathways and potential therapeutic targets. Cross-sectional studies of serum proteome at diagnosis of T1D have suggested, not surprisingly, involvement of inflammation and innate immunity. However, samples used in these studies were collected shortly after T1D diagnosis, reflecting late stages of  $\beta$ -cell destruction and hyperglycemia. In contrast, prospective cohorts allow profiling of the proteome as children develop IA and progress to T1D and in aged-matched controls. Several published and unpublished discovery studies have generated multiple protein candidates, but little consistency. This highlights the need for replication in larger studies, able to control for heterogeneity of pre-T1D phenotypes and confounders, e.g., age and sex, but also for genetic background and environmental exposures. DAISY has collected a unique dataset and serum/plasma samples for the high-power targeted protein analysis proposed below. The goal of this study is to help form consensus regarding proteomic biomarkers of IA and T1D and underlying pathways. The analytical platform proposed here is capable of quantification of low-abundant proteins, likely to be found in the earlier stages of disease, that can be masked by more abundant proteins.

[figure not shown]
**INNOVATION:** So far, none of the 'omics biomarkers reported to predict progression from IA to T1D have been confirmed by independent studies. Using targeted proteomics we will validate candidate peptides/proteins reported from several discovery studies. The analyses will cover an

unprecedented age-span of diabetes diagnosis (0-25 y) while controlling for an apparent heterogeneity of IA phenotypes, age, sex and ethnicity.

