SNPs and ImmunoChip's >200,000 SNPs in non-Hispanic white participants with HLA-DR3/4. In a separately funded Helmsley Trust project, DAISY will apply the whole genome sequencing (WGS) by Illumina X Ten sequencing (MacroGen, Rockville, MD) to the 213 cases and controls included in Specific Aim 2. The interpretation of WGS results will be informed by the results of the Type 1 Diabetes Genetic Consortium (T1DGC) WGS (also by MacroGen) and genetic architecture of T1D. The analyses will be performed by Dr. [name], from the Center for Public Health Genomics at the University of Virginia and past PI of the T1DGC. His lab has completed the DAISY ImmunoChip analyses and we also collaborate on TEDDY. **Dietary and infectious exposure** data collected by DAISY will be used in the analyses as a distinct set of features to explore in relation to the above 'omic domains.

Hypotheses: A limited number of features and time-points derived from high-resolution 'omics data can reliably predict, on an individual basis, 3.1: development of IA; and 3.2: the rate of progression from IA to T1D

**Preliminary Evaluation** As a proof-of-principle, modeling was performed on data from the DAISY1 (Table 3) nested case-control study of subjects who developed diabetes (T1D, n=25), persistent IA but not T1D (IA+, n=20), and 25 healthy age-matched controls. Four time points were studied: T1-the earliest available sample, T2-just prior to IA, T3-just after development of IA, and T4-prior to diagnosis of T1D or the most recent. Demographics (age, sex, ethnicity, family history of T1D), genetic (HLA-DR,DQ and 108 non-HLA SNPs), immune, metabolic and proteomic biomarkers were compared between the groups across the 4 time points.

Metabolites The global metabolic profiling combined three independent *platforms*: ultrahigh performance liquid chromatography/tandem mass spectrometry optimized for basic and acidic species, and gas chromatography/mass spectrometry (Metabolon, Durham, NC). A total of 382 named metabolites were included in this analysis. An example of this study results is shown in **Figure 7**.

BIOCHEMICAL	T1			T2			T3			T4		
	AbPos	T1D	T1D	AbPos	T1D	T1D	AbPos	T1D	T1D	AbPos	T1D	T1D
Cofactors and Vitamins	C	C	AbPos	C	C	AbPos	C	C	AbPos	C	C	AbPos
Vitamin C	0.63	0.41	0.66	1.67	1.46	0.55	1.01	0.75	0.75	0.63	1.12	1.55
threonate	0.94	0.7	0.75	1.02	1.07	1.05	1	1.02	1.04	1.01	0.94	0.93

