Statistical analyses will be carried out by [name] (PNNL) – see letter of collaboration. The relative quantification data will be normalized to the reference sample, log transforming (base 2), and then median centered. First mixed effects linear models, with a normal conditional distribution and identity link function, will be fit separately to cases and controls using R and the lme4 package. Age and sex will be used as the fixed effects in these models including linear and quadratic models to examine trends in abundance over time and random effects for each subject will be included to account for the subject variability and non-independent nature of the data over time. Likelihood ratio tests will be conducted with ( $\alpha = 0.05$ ). A difference in trends between cases and controls will be quantified by fitting the mixed effects linear/quadratic models and including a fixed effect to account for different mean intercepts, slopes and quadratic terms, where applicable, for each group. Additionally, a likelihood ratio test between a model including and not including case-control status as an effect can be used to determine differences in intercept, slope, and/or quadratic mean trends. The highest degree model that is statistically significant for at least one group will be fit with fixed effects for age and group and an interaction term between age and group (allowing for separate slopes for each group) and a random effect for subject.

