Detecting a significant difference in trends cases and controls is by testing if the group regression parameter is equal to 0, which is rejected when the true population parameter is different from 0. In the case of a linear trend, this involves the following t-test:  $t_{\alpha, n-4} = b/s_b$  where  $\alpha$  is the type 1 error rate,  $b$  is the estimated regression parameter,  $s_b$  is the standard error of the regression parameter estimate. The standard error of the regression parameter estimate depends on the overall variability of the data, the number of subjects (n) and the number of time points per subject (T). A power analysis was conducted based on a simulation study. From the previous DAISY1 study, the 75th percentile absolute value estimated slope due to group membership was  $b = 0.005$  and the overall error variances were calculated for each peptide. **Table 4** gives the power of the above test for select combinations of number of subjects and time points per subject for the 90th percentile of error variances. There will be a sufficient power to test the hypotheses with 4 or more samples per subject even in a subgroup analysis with 25 subjects per subgroup. For instance, a sample size of 20 subjects per group and 4 time points per subject will provide at least 82% power at the 90th percentile of the observed error variances.

Number of subjects/group	Number of time points/subject					
	3	4	5	6	7	8
30	.89	.99	1	1	1	1
25	.77	.90	.96	.99	1	1
20	.60	.71	.82	.89	.95	.98
15	.34	.43	.57	.52	.70	.84

The mixed model approach is typically preferred to ANCOVA with repeated measures for this type of data. ANCOVA's limitations include sensitivity to missing observations and restrictive variance-covariance structures. Additionally, mixed models naturally handle uneven spacing of

repeated measurements, tend to be more interpretable and will lead to natural tests for comparing groups.

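### The Aim 2 protein models compare cases and controls on age alone, so they cannot tell a protein that precedes islet autoimmunity from one that changes after it, and they blunt changes tied to seroconversion

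*Protocol*

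**What the plan says.** The analysis is set out in the protocol, Data Analysis Plan (IV.F), Specific Aim 2. Models are first fitted to cases and controls separately: "Age and sex will be used as the fixed effects in these models including linear and quadratic models to examine trends in abundance over time", with a random effect per subject. The comparison model then has "fixed effects for age and group and an interaction term between age and group". A likelihood ratio test with and without case-control status "can be used to determine differences in intercept, slope, and/or quadratic mean trends". The only power calculation is for a group difference in slope.

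Elsewhere the protocol places time relative to IA:

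- Research Plan, Specific Aim 2, Significance, gives the purpose as "Prospective evaluation of the proteome contemporary with development of IA, or progression to T1D". Hypothesis 2.1 is that proteins predict development of IA.
- Specific Aim 3, Preliminary Evaluation, defines the DAISY1 pilot samples relative to IA: "T2-just prior to IA, T3-just after development of IA", with an earliest sample (T1) and a last sample (T4) on either side.
- Preliminary Studies reports how widely onset varies: "Early-onset IA developed in 143 subjects; late-onset IA developed in 65", split at age 7. Specific Aim 1, Significance, says IA can start at any age up to 15.

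For Aim 2 itself, the readable text says only that four time points per subject will be analysed. The layout is in Figure 6, which is not shown.

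**The concern.** A change linked to seroconversion happens at a different age in each child. A common line or parabola in age averages it over children who have and have not yet seroconverted.

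The first consequence is interpretive. If the group test rejects, the result may reflect a protein that differed before IA, or one that moved only once IA was present. Hypothesis 2.1 concerns the former. The protocol has grounds to care: of the 142 DAISY2 candidates, 31 are reported as differing before autoantibodies appeared, and the Aim 2 model has no term that could confirm this.

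The second consequence is loss of power and shrunken estimates for changes timed to IA.

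**Working it through.** **The plan's own figure.** The protocol powers the slope test on b = 0.005. It gives neither the time unit nor the error variance, so its power cannot be reproduced. The text states at least 82% for 20 subjects per group and 4 time points, where Table 4 shows .71; .82 is the 5-point cell. That is a separate discrepancy and does not bear on this point.

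**Inputs from the protocol.** 213 cases and 213 controls; four samples each; early onset in 143/(143 + 65) = 143/208 = 69%; onset up to age 15; α = 0.05.

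**Assumptions.** Samples timed as T1–T4 in DAISY1; controls with the same age distribution; effect 0.3 residual SD; between-child SD equal to residual SD, so ICC = 1/(1 + 1) = 0.5.

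**Models compared**, each with a random intercept per child:

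- Age-based: y = β₀ + β₁·age (+ β₂·age²) + γ₀·G + γ₁·G·age (+ γ₂·G·age²). The overall test sets all γ = 0, with 2 df (linear) or 3 df (quadratic).
- Aligned: y = position (T1–T4) + age + age² + G × position. The test of the group terms has 4 df.

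Power = P(χ²_df(λ) > χ²_df,0.95), where λ is the drop in generalised least squares residual sum of squares, computed on the true means, when the group terms are added. Monte Carlo gave the same picture, with null rejection of 4.5–5.5% for all three tests.

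| True pattern in cases | Age, linear | Age, quadratic | Aligned |
|---|---|---|---|
| Lasting shift from IA onward | 54–56% | 49–52% | 77–78% |
| Shift from the pre-IA sample onward | 71–72% | 72–73% | 78–80% |
| Transient change around IA | 22% | 32–33% | 78% |
| Constant difference, 0.3 SD | 70% | 63% | 58% |
| Divergence of 0.03 SD per year of age | 72–81% | 65–75% | 49–60% |

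Ranges cover repeat runs with different detailed visit ages.

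**Slope test alone.** For a transient change, the group-by-age slope test, which is the one the protocol powers, rejects about 5–6% of the time, close to its size.

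**A second set-up** used a bell-shaped peak at seroconversion (SD 0.5, 1 or 2 years; ICC 0.3 or 0.6), with its height chosen to give the aligned test 90% power:

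- slope test: about 5%;
- slope plus quadratic terms: 17–27%;
- overall linear test: 25–72%;
- overall quadratic test: 37–74%.

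The age model's fitted group difference just after seroconversion was 0.42–0.69 of the peak height, where the truth was 0.86–0.99. That is 0.42/0.86 = 49% to 0.69/0.99 = 70% of the true value.

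**Interpretation.** The first row of the table also shows the problem for Hypothesis 2.1. A protein that changes only after IA still makes the overall age-based test reject roughly half the time, and nothing in that model marks the result as post-IA.

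**The case against.** Four points on the other side carry weight.

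1. **Sample timing.** A reader might infer that the Aim 2 samples are anchored to seroconversion. The readable text documents this only for DAISY1, so here it is an assumption pending Figure 6.
2. **The target.** A reader might infer that the study sets out to validate a peak at seroconversion. It does not say so. Hypotheses 2.1 and 2.2 concern prediction of IA and the rate of progression to diabetes, and a peak is one possible pattern among several.
3. **The size of the loss.** A reader might conclude that IA-related markers are largely missed. That is true of the slope test for a transient change. It is not true of the whole plan, because the optional likelihood ratio test includes the group intercept. It loses little for a shift that begins before IA and keeps about half its power for a lasting post-IA shift.
4. **The age axis has merit.** For a constant difference or a divergence with age the planned model is the more powerful. Replacing it would trade one set of alternatives for another.

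Aim 3 also uses these proteomic data, and its preliminary work compared groups at T1/T2 and T3/T4. That shows position-based comparison is feasible, but it is pilot work for another aim and does not enter the Aim 2 tests.

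These points limit the claim about power. They leave the interpretive gap untouched: whatever the effect size, the Aim 2 model has no term separating pre-IA from post-IA samples.

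**Conclusion.** The point stands as a gap to be filled. Age is not a wrong axis. As written, the Aim 2 models cannot distinguish a protein that precedes IA from one that follows it, and they attenuate changes tied to seroconversion. The attenuation is severe for a transient change (22%/33% against 78%), moderate for a lasting post-IA shift (about 55%/50% against 78%) and small for a shift already present before IA (about 72% against 78–80%).

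These figures rest on DAISY1-type sample timing, a 0.3 residual SD effect and an ICC of 0.5, none of which the protocol gives for Aim 2. The interpretive gap needs only the stated model and the spread of onset ages.

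**What to change.** Keep the age, group and age-by-group model. In the Data Analysis Plan, Specific Aim 2, add one prespecified analysis:

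- **Time term:** years from first positive antibody, or sample position (pre-/post-IA, T1–T4), with its interaction with group, adjusted for age (linear and quadratic) and sex, with a random effect for subject.
- **Controls:** give each an index age drawn from the case distribution of seroconversion ages within matching strata. The protocol frequency-matches on age, sex and ethnicity but defines no strata, so these must be written down.
- **Hypothesis 2.1:** base it on the group contrast in the pre-IA samples.
- **Sample timing:** state the Aim 2 sampling points in the text as well as in Figure 6.

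No new assays are needed. The costs are that the control index age is a convention, and that each of the roughly 75 proteins has one further test to be covered by the multiplicity control.

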**APPROACH:** We will characterize differences in the abundances/profiles of ~75 target proteins in a nested case-control study of 213 youth persistently positive for IA and 213 controls, frequency matched on age, sex and ethnicity (79% NHW). As of 9/2015, 89 cases have developed T1D (at mean age  $9.6 \pm 4.6$  y), 61 were persistently positive for  $\geq 2$  islet autoantibodies or one high-affinity autoantibody and 63 were positive for one low-affinity autoantibody (**Figure 6**). These three subgroups of youth represent heterogeneity of the IA phenotypes that show, respectively, rapid, slow and no progression to T1D (see Figures 4 and 6, above).

**Hypothesis 2.1:** A reproducible set of proteomic biomarkers will predict development of IA independently of demographic factors and HLA class II genotypes.

**Hypothesis 2.2:** A reproducible set of proteomic biomarkers will predict the rate of progression from IA to T1D independently of demographic factors, HLA class II genotypes.

**Figure 6:** Proposed nested case-control study of targeted proteomics.

Serial samples collected at 4-time points per subject will be analyzed.

**Preliminary data:** Two nested cases-controls DAISY proteomics discovery studies have identified proteins associated with development of IA and/or progression to T1D (**Table 3**). In **DAISY1**, one of the 4 proteins identified by the aptamer-based approach as strongly associated with IA and T1D (CNDP1,  $p=1.22e^{-07}$ , q-value 0.00013) was independently confirmed in a different laboratory using the LC-MRM/MS approach.

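### The Aim 2 case-control trend model names only one random effect per subject, so its slope-difference test exceeds the nominal 5% if protein slopes vary between children

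*Protocol*

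**What the plan says.** The Aim 2 text of protocol section IV.F (Data Analysis Plan) proceeds in two steps.

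- **Separate fits.** Linear and quadratic mixed models are fitted to cases and to controls in lme4, and "random effects for each subject will be included to account for the subject variability and non-independent nature of the data over time". The kind of random effect is not named.
- **Group comparison.** The highest-degree model that is significant in at least one group is refitted with age and group as fixed effects, and the sentence continues "and an interaction term between age and group (allowing for separate slopes for each group) and a random effect for subject". Here the random effect is singular.

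The paragraph sets alpha at 0.05 for its likelihood ratio tests. It also allows a likelihood ratio test on case-control status covering intercept, slope or quadratic differences.

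For power, "In the case of a linear trend, this involves the following t-test", namely b divided by its standard error. That standard error is said to be one that "depends on the overall variability of the data, the number of subjects (n) and the number of time points per subject (T"). Table 4 comes from a simulation using the overall error variances of the DAISY1 peptides, and power is called sufficient "even in a subgroup analysis with 25 subjects per subgroup".

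The design section for Aim 2 describes the differences to be studied "in a nested case-control study of 213 youth persistently positive for IA and 213 controls", with serial samples at 4 time points. It divides the cases into three subgroups that progress to diabetes rapidly, slowly or not at all.

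**The concern.** The quantity tested is a difference in slopes, so the independent replicates are children, not samples. A random intercept lets children differ in level but gives every child in a group the same underlying slope. Any real variation in slope is then absorbed into residual error and treated as if it averaged out over all the samples. The standard error of the age-by-group term is too small and the test rejects too often.

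The protocol itself gives reason to expect slope variation. The case group deliberately mixes three progression phenotypes, and Hypothesis 2.2 holds that proteins predict the rate of progression. The protocol also faults repeated-measures ANCOVA for restrictive covariance structures, yet a lone random intercept imposes compound symmetry, which is itself restrictive.

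Aim 2 is a validation study, motivated by earlier 'omics markers that were not independently confirmed. Excess false positives in its trend tests would work against that purpose.

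**Working it through.** **Inputs from the protocol:** alpha 0.05; T = 4 time points; 213 per group, with 25 per subgroup as the size called adequate; one random effect for subject; Table 4 power of .90 at 25 per group and 4 time points.

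**Assumed:** two-sided testing (not stated), and the between-child slope variance τ², which is not given. Write σ² for the residual variance, Sxx for the within-child sum of squares of age, and r = τ²·Sxx/σ². The range shown is r = 0 to 2.

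**Formula (balanced times, random intercept only).**

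- True variance of one child's slope: σ²/Sxx + τ².
- The fitted residual variance absorbs the slope variation over T − 1 within-child degrees of freedom, so the reported variance is σ²/Sxx + τ²/(T − 1).
- True/reported = (1 + r)/(1 + r/(T − 1)), which at T = 4 is (1 + r)/(1 + r/3).
- Type I error = 2Φ(−1.96/√ratio).

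**Results at T = 4.** The first row reproduces the plan's own alpha.

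| r | variance ratio | reported SE / true SE | type I error |
|---|---|---|---|
| 0 | 1.00 | 1.00 | 5.0% |
| 0.1 | 1.1/1.033 = 1.06 | 0.97 | 5.8% |
| 0.25 | 1.25/1.083 = 1.15 | 0.93 | 6.8% |
| 0.5 | 1.5/1.167 = 1.29 | 0.88 | 8.4% |
| 1 | 2/1.333 = 1.50 | 0.82 | 11.0% |
| 2 | 3/1.667 = 1.80 | 0.75 | 14.4% |

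The ratio cannot exceed 3, so the ceiling is about 26%. The number of children does not appear in the formula.

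**Simulation check** (random intercept fit, T = 4, t-test on total subjects minus 4 degrees of freedom):

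| Setting | r = 0 | r = 0.25 | r = 1 | r = 2 |
|---|---|---|---|---|
| 25 per group, common ages | 4.2% | 6.2% | 10.9% | 13.8% |
| 213 per group, common ages | 6.1% | 6.8% | 11.7% | 15.9% |
| 25 per group, child-specific ages | 4.8% | 6.9% | 12.7% | 18.2% |
| 213 per group, child-specific ages | 5.2% | 7.6% | 13.9% | 20.3% |

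The excess persists at the full sample size and is somewhat larger when ages differ between children.

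**With a random age slope added** (child-specific ages, 400 to 600 replicates), rejection was 5.0% and 5.8% at 25 per group, and 6.0% and 3.3% at 213 per group, for r = 0.25 and 1. That is near nominal, given so few replicates.

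**Power.** Table 4 cannot be reproduced, because neither the error variance nor the time spacing is given. Suppose the .90 at 25 per group and 4 time points was simulated without slope variance. With the correct standard error it becomes Φ((1.96 + 1.28)/√(1 + r) − 1.96), which is .83 at r = 0.25, .63 at r = 1 and .47 at r = 2.

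**The case against.** The strongest reply is that the protocol never uses the word intercept. A random effect for subject may only name the grouping factor. The preceding fits use the plural, nothing says the random structure was then reduced, and the stated preference for mixed models over restrictive covariance structures would sit oddly with a deliberate compound-symmetry model. Random-effects detail is also often left to a statistical analysis plan, which is not at hand here.

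Part of this stands: the intent may have been broader than the words, and an analysis plan that names a random slope would settle the model. But the sentence defining the tested model is singular, the plural wording names no slope either, and the power text ties the standard error only to overall variability, number of subjects and number of time points. The protocol chose to fix the model, the test and the power basis, and what it fixed omits slope variance.

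A reader might also infer more than the protocol supports:

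- **That the test is known to be inflated by a given amount.** It is not. With little slope variation the error stays close to nominal, and r is undocumented.
- **That about 13 to 22 false positives, instead of 7.5, should be expected among 150 peptides at r = 0.5 to 2.** The arithmetic (150 × 0.084 and 150 × 0.144, against 150 × 0.05) requires every peptide to be null, to share one r and to be tested without correction. The targets are chosen because earlier studies found them significant, and the 150 peptides represent about 75 proteins.
- **That this p-value alone decides validation.** No section says so. Intercept differences are tested too and are not affected in the same way, and Hypotheses 2.1 and 2.2 concern prediction.

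**Conclusion.** The point holds conditionally. As written, the group-comparison model is a random-intercept model. If slopes vary between children, its slope-difference test exceeds the stated alpha: about 6% to 8% for modest variation (r = 0.1 to 0.5) and 11% to 14% for r = 1 to 2, at 4 balanced time points. These figures rest on an assumed r, two-sided testing and the natural reading of the model sentence. Slope variation is plausible from the protocol's own description of the cases but is not quantified there. The finding is limited to the slope-difference tests and to the power statement built on the same variance. It is worth correcting because the change is small and the weakness lies in a method the protocol states.

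**What to change.** In section IV.F, Specific Aim 2:

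1. State that the group-comparison model has a by-subject random intercept and random age slope (in lme4, age within subject). Where the slope variance is estimated at zero, the model reduces to a random intercept.
2. A random linear slope does not cover between-child curvature. Where a quadratic model is selected and 4 samples per child cannot support a random quadratic term, use subject-clustered robust standard errors for the group-by-age terms.
3. Rerun the Table 4 simulation under that model, with between-child slope variance over a stated range, and report the error variance and time spacing used. The rerun should also settle the text's 82% for 20 subjects and 4 time points, where Table 4 shows .71 (.82 is the entry for 5 time points). The present point does not depend on that mismatch.

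The cost is one model term, a rule for quadratic models and one rerun of the simulation, with no new data. Some of the peptide models may give boundary fits, which the rule in item 1 covers. If slopes do vary, stated power will be somewhat lower, chiefly for the small subgroup sizes that Table 4 covers.
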